9.4.3 Sample size for MRI/MRS biomarkers

For imaging measures, we will have data for all subjects. Assuming a 10% missing data rate we have 80% power to detect a difference in the mean of secondary outcomes across treatment groups of 0.26 SDs. For the inflammation and brain injury biomarkers, we will have a total of 200 subjects and have 80% power to detect a mean difference across the treatment groups of 0.4 SDs.

9.4.4 Sample size for plasma biomarkers of brain injury and inflammation

A sample size of 91 neonates per group would have been required to detect a 0.5 SD difference on the log scale with a single observation per neonate with 80% power while controlling for a Type I error of 0.0125 (4 markers, Bonferroni). However, since we have 4 samples per neonate, a sample

size of 100 neonates per treatment group (with 400 samples per group, but correlated) will be more than sufficient to attain >80% power.

9.4.5 Achieving the sample size

The plan is to enroll and randomize 500 patients over a 36-month period. The 17 sites that were included in the original study proposal cooled a total of 530 HIE infants in the year 2014. From the NEATO phase II randomized controlled trial study, we estimate that at least 40-45% of these infants would be eligible and will consent for a phase III trial, yielding at least 16 enrolled infants per month. With a further conservative estimate of 14 per month allowing for slower enrollment during start-up, we can enroll 500 patients in 36 months.

9.5 DATA MONITORING

We will monitor the accuracy of data entry by the sites both internally and externally. We will review study data on arrival for completeness. We will then subject each submitted data set to a set of preliminary checks to search for values that are out-of-range or otherwise inappropriate. Using the Patient Monitoring Report, a subset of all data points in the CRFs will be compared with the medical record for 20-25% of enrolled subjects. Any outstanding data queries will be resolved with the research coordinator at the time of the site-monitoring visit. After each study site monitoring visit, a report will be prepared and copies sent to the Study File, the study PIs ([name] and [name]), the site PI, and the site coordinator. The quality and completeness of other deliverables (blood samples, MRIs) will be monitored.

9.6 DATA AND SAFETY MONITORING PLAN (DSMP)

The DSMB will review the accruing data to: 1) ensure that the study is adequately enrolling; 2) to ensure that there are no serious safety concerns; and 3) to assess whether the study efficacy appears overwhelming. The DSMB will be assigned by NINDS. The research coordinator at each site will monitor each subject weekly for the presence of any complications. Serious adverse events will be brought to the attention of the DSMB, and if appropriate, the IRB, in writing. An independent medical monitor will review all cases of serious adverse events.

As part of this DSMP, we will perform continuous and interim analysis of accruing safety data. We have defined potentially treatment (Epo) related serious adverse events (SAEs) that will be monitored throughout the course of the study. Specifically, for SAEs we will compare absolute rates to expected rates based on published data for similar newborns, and will seek careful DSMB review and guidance when observed rates exceed pre-specified thresholds. In addition, at planned interim analysis we will formally compare the event rates across the two treatment groups using appropriate small sample methods such as Fisher's exact test. The DCC PI will remain masked to assignment while the study staff statistician will not.

The primary outcome of the study is a composite endpoint of mortality or NDI at 24 months of age. Therefore, monitoring the primary outcome for treatment efficacy or futility is challenging. Based on enrollment plans, the majority of patients will have been randomized by the time NDI is assessed at 24 months for any participants, and therefore we do not expect to be able to conduct a first interim analysis prior to the completion of enrollment. We expect to have the primary outcome evaluated on the first quarter of subjects (n=125) after 34 months of recruitment at which point we expect to have randomized n=450 of the total n=500 subjects (90% enrollment completed). Therefore, any actions that a DSMB might take to prevent subsequent patients from receiving an ineffective treatment (futility) or to make available a useful treatment (efficacy) will not have a direct impact on patients participating in

this study. As a surrogate for long-term 24-month clinical efficacy on NDI, one alternative would be to monitor directly early MRI results as intermediate outcomes or surrogates. However, a large study published by Cheong et al.,¹⁵⁰ found that early MRI measurements had poor sensitivity (27-60%) for accurately predicting death or NDI at 2 years. Therefore, we do not recommend using early MRI measures as a surrogate for the long-term outcome for monitoring treatment efficacy. Given that we are not conducting interim analysis directly on the primary outcome measure for efficacy or futility, we do not make adjustments to sample size or statistical power to account for interim alpha spending.

Our primary objective for interim analyses is therefore to allow for careful and continued monitoring of mortality and safety outcomes. We propose to conduct formal statistical analysis and inference for mortality at three interim and one final analysis time. We will continue to present mortality and SAE data from all available follow-up data, but we expect most treatment-related safety events to occur within the first three months of follow-up. We will conduct formal safety evaluation at 6, 12, 18, and 24 months following the start of enrollment, where approximately 25, 50, 75, and 100% of the study cohort will have been randomized and followed for at least 3 months. As part of each interim analysis, we plan to monitor mortality as a primary safety endpoint and will control the overall significance level using O'Brien-Fleming boundaries (net alpha=0.05 significance, accounting for three interim and one final analysis). The DSMB will also monitor all other SAEs utilizing the same O'Brien-Fleming sequential monitoring boundaries without further adjustment for multiple comparisons, but allowing for flexibility to continue the study if the O'Brien-Fleming boundary is reached on a secondary SAE endpoint.

Table 11. O'Brien-Fleming Monitoring Boundaries

Enrollment	Monitoring p-value: Death
25%	0.000014734
50%	0.0030359
75%	0.016248
100%	0.030701

EXAMPLE SAFETY MONITORING TABLE

Shell Table 1. Closed Report: Serious adverse event (SAE) incidence rate (number of events/number at risk) and threshold for action.

Serious Adverse Events	Group A	Group B	Expected (Range)	Threshold for Action	p-value*
Systemic hypertension			0.2-3.0 ¹⁵¹⁻¹⁵³	6%	
Polycythemia			1.0-5.0% ¹⁵⁴	10%	
Disseminated intravascular coagulation (DIC)			11.0-45.0% ³⁻⁷	50%	
Major venous or arterial thrombosis			0-2.0% ^{4,6,155}	8%	
Pulmonary hypertension			6.0-22.0% ^{3,4,7,156}	30%	
Intracranial hemorrhage			7.9-31.3% ^{6,7}	37%	
Cardiopulmonary arrest			0.002-0.13% ¹⁵⁷	5%	
Other unexpected life-threatening event			1.0% ⁴	5%	

Death			8.1-35.1% ³ 7,155,158,159	40%	
--------------	--	--	---	-----	--

* P-value calculated for the rate ratio comparing treatment Group A to Group B.

In addition, we will provide a table comparing complications of HIE between the groups.

Data Safety Monitoring Schedule: Our target enrollment is n=500 which is expected to accrue during the first 4.0 years of the trial. Therefore, we will enroll approximately 83 subjects every 6 months. Our planned DSMB safety analyses will occur every 6 months after trial initiation. At the first safety evaluation, we expect to have 83 subjects enrolled, but would only have discharge outcomes on the first 60 subjects. Each subsequent 6-month period would increase the number of babies by 83 leading to the following cumulative number of subjects available for analysis. Safety evaluation will be based on all available follow-up but we expect the majority of SAEs and AEs to occur during the neonatal hospitalization and therefore within one month of age (2-4 weeks) in the majority of cases.

Table 12. Cumulative number of subjects evaluated for safety events and for the long-term efficacy outcome

Month	6	12	18	24	30	36	42	48	54	60	.66
Safety (1 mo)	60	143	226	309	392	475	500				
Efficacy (24 mo)	0	0	0	0	60	143	226	309	392	475	500

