9.4 SAMPLE SIZE AND ACCRUAL

9.4.1 Primary Outcome Sample Size Calculations:

Our proposed HEAL sites report an overall mortality rate of 14%. Using three large sites that participated in the phase II study (UCSF, Wash U, CNMC) we can also estimate the rates of neurodevelopmental impairment: death = 14%; moderate-severe impairment = 18%; mild impairment = 17%; and normal = 51%. Therefore, we anticipate a **control primary outcome rate of 49%** (death or NDI).

Non-human data informing treatment effect size: A recent study with nonhuman primates (*Macaca nemestrina*) compared animals experiencing 15-18 minutes of umbilical cord occlusion that were then treated with either saline (n=14), therapeutic hypothermia (n=9), or therapeutic hypothermia and multiple doses of Epo.²¹ Among animals treated with saline 8/14 = 57% died or had NDI. Among animals treated with hypothermia (HT) alone 7/9 = 78% died or had NDI, while among animals treated with hypothermia and Epo (HT+Epo) only 5/12 = 42% were observed to die or have NDI. Results from Figure 2 of Traudt et al.¹⁴⁹ (2013) show the number of animals in each outcome category by treatment group. These data suggest a risk ratio of 0.53 (95% CI: 0.25, 1.14) comparing HT+Epo to HT alone, and a risk ratio of 0.73 (95% CI: 0.32, 1.64) comparing HT+Epo versus saline. Therefore, animal data support an Epo effect that optimistically corresponds to a

50% reduction, and that is conservatively associated with a 27% reduction in the primary outcome rate.

Phase I data informing treatment outcome rates: Given that the primary outcome is based on a 22-26 month assessment we can rely on a recently completed long-term follow-up from a phase I study⁸⁴ in which 24 cooled infants were given multiple doses of Epo ranging from 250U/kg to 2500U/kg²⁴. At 22-26 months of age n=22 subjects were followed, and 0/22 subjects died, 1/22 had moderate-severe NDI, and 6/22 had mild NDI. This study suggests an **overall primary outcome rate of 7/22 = 31.8%** (exact confidence interval = 14%-55%) for our planned intervention group. We recognize that the dosing of Epo was not optimized in the phase I trial, and our proposed study will use multiple doses of 1000U/kg for all subjects which has been shown to yield plasma concentrations observed to be neuroprotective in animal studies.

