### 1.2 Design

This study is a randomized parallel group double-masked, placebo-controlled trial in neonates with HIE. We will enroll 500/2 = 250 subjects in each of two treatment groups: Epo-treated vs. placebo control. Eligible neonates will be enrolled and treated with either Epo or normal saline (on study day 1,2,3,4, and 7) and followed for a fixed period of 24 months ( $\pm 56$  days) for survival and neurological outcomes. For extenuating circumstances, for example, COVID-19 restrictions, the in-person elements of the final endpoint evaluation may be performed up to 36 months of age. The follow-up period was chosen to provide meaningful motor and cognitive outcomes, since CP and motor and cognitive deficits are more reliably diagnosed at 2 years of age. Enrolled children will be randomized, stratified by study site and severity of HIE, with equal likelihood to receive Epo or saline.

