## 5.5 Safety Data

Clinical safety data includes serious adverse events (SAEs) and clinical laboratory markers both from the hospitalization and study intervention period and from the long-term follow-up period. Because these are critically ill newborns, we anticipate that most safety events will occur during the initial inpatient and treatment period. Safety event rates will be tabulated by study group and compared separately for each SAE using a multivariable logistic regression model, with adjustment for randomized treatment group, and randomization stratification factors of clinical recruitment site and HIE severity (moderate/severe). We will additionally create a per-patient aggregate count of SAEs and evaluate the rates between groups using a Poisson regression model with robust standard errors and adjustment for randomization stratification factors. For any safety events that occur infrequently (<2%), we will use Fisher's exact test to compare the rates between treatment groups. All safety events identified post-birth will be included in the primary analysis, while the secondary analyses will evaluate safety events occurring post-treatment with the first study drug dose as well as those events assessed as being possibly related to the study drug. Statistical significance is defined conservatively at the alpha=0.05 level with no correction for multiple outcomes.

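### The interim mortality test is not fixed, and the one example named, an unstratified Fisher's exact test, would hold overall error to about 3 to 4% instead of 5% even with correct cut-offs

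*Protocol*

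**What the plan says.** Protocol 9.6 and SAP 9 make mortality the primary safety endpoint. It is tested formally at four looks, when "approximately 25, 50, 75, and 100% of the study cohort will have been randomized and followed for at least 3 months". The error target is "net alpha=0.05 significance, accounting for three interim and one final analysis", and Protocol Table 11 (SAP Table 6) labels its four entries as monitoring p-values for death.

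The test behind those p-values is described in more than one way:

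- **Interim comparison of event rates (Protocol 9.6, SAP 9):** "we will formally compare the event rates across the two treatment groups using appropriate small sample methods such as" Fisher's exact test. Stratification is not mentioned.
- **DSMB shell table (Protocol 9.6, footnote):** "P-value calculated for the rate ratio comparing treatment Group A to Group B".
- **Safety analysis outside the monitoring plan (Protocol 9.3.4, SAP 5.5):** events are "compared separately for each SAE using a multivariable logistic regression model", adjusted for site and HIE severity, with Fisher's test kept for events below 2%.

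On the design, SAP 1.2 says "Enrolled children will be randomized, stratified by study site and severity of HIE". On the expected rate, Protocol 9.4.1 says "Our proposed HEAL sites report an overall mortality rate of 14"%.

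**The concern.** At 14% mortality, deaths are not rare by the plan's own 2% rule. The looks hold 125 to 500 infants, so about 17 deaths are expected at the first (0.14 × 125 = 17.5) and 70 at the last. Two features would make an unstratified Fisher test reject less often than its nominal level:

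- It is discrete and conditional, so its actual size lies below nominal.
- Randomisation balances the arms within severity. If severity predicts death, the true variance of the difference is the within-severity variance, while a pooled test uses the larger total variance.

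Both errors run in the direction that matters in safety monitoring: a real excess of deaths is less likely to cross the boundary at a given look. The test that the DSMB sees could also differ from the test of the same event in the final report.

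**Working it through.** **1. What Table 11 contains.** Inputs: alpha 0.05, looks at t = 0.25, 0.50, 0.75, 1 (Protocol 9.6). The O'Brien-Fleming-type spending function is α(t) = 4·[1 − Φ(2.2414/√t)], where 2.2414 is the 0.9875 normal quantile.

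| t | cumulative α(t) | increment | Table 11 |
|---|---|---|---|
| 0.25 | 0.0000147 | 0.000014734 | 0.000014734 |
| 0.50 | 0.0030506 | 0.0030359 | 0.0030359 |
| 0.75 | 0.0192986 | 0.016248 | 0.016248 |
| 1.00 | 0.0500000 | 0.030701 | 0.030701 |

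The match is exact. The table therefore lists alpha *spent at* each look of a two-sided 0.05 plan, not p-value cut-offs. Numerical integration over the four looks gives an overall error of 0.037 when the entries are used as cut-offs with a correctly sized test. The nominal cut-offs that give 0.05 are about 0.000015, 0.0030, 0.018 and 0.044.

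**2. Fisher alone, no severity effect.** Exact four-look calculation at 14% mortality in both arms, overall two-sided error:

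| Arms | Test | Nominal cut-offs | Table 11 entries |
|---|---|---|---|
| 62/62, 125/125, 187/187, 250/250 | Fisher | 0.036 | 0.027 |
| 62/63, 125/125, 188/187, 250/250 | Fisher | 0.037–0.038 | 0.029 |
| 60/65, 123/127, 186/189, 248/252 | Fisher | 0.043 | 0.031 |
| 62/63, 125/125, 188/187, 250/250 | mid-p | 0.048 | 0.037 |

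Over the shell table's published death range (8.1 to 35.1%), Fisher gives 0.035–0.041 with nominal cut-offs and 0.026–0.030 with Table 11.

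**3. Adding severity (assumed values).** The documents give neither the severe share nor death by severity. Take 25% severe, with rates averaging 14%. With arms balanced within severity, the ratio of true variance to the variance a pooled test uses is [0.25·p_s(1−p_s) + 0.75·p_m(1−p_m)] / (0.14 × 0.86):

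- 28%/9.3% (severe/moderate): (0.0504 + 0.0634)/0.1204 = 0.95
- 35%/7%: (0.0569 + 0.0488)/0.1204 = 0.88
- 44%/4%: (0.0616 + 0.0288)/0.1204 = 0.75

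Simulated overall error (25,000 trials; 17 equal sites and blocks of 4 within site and severity, both assumed), Fisher against severity-stratified Mantel-Haenszel (MH):

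| Severe/moderate | Nominal: Fisher | Nominal: MH | Table 11: Fisher | Table 11: MH |
|---|---|---|---|---|
| 14%/14% | 0.043 | 0.050 | 0.032 | 0.038 |
| 28%/9.3% | 0.036 | 0.048 | 0.026 | 0.037 |
| 35%/7% | 0.029 | 0.047 | 0.021 | 0.035 |
| 44%/4% (extreme) | 0.018 | 0.044 | 0.012 | 0.032 |

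Repeat simulations of the 35%/7% split put Fisher with nominal cut-offs between 2.6% and 3.3%.

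**4. Detection of excess deaths.** No severity effect, 24% against 14%, Table 11 entries, probability of crossing for harm by looks 2/3/4:

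- Fisher: 0.14/0.50/0.74
- mid-p: 0.17/0.52/0.77
- Pearson: 0.17/0.53/0.77

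The loss is about 2 to 4 points. At 28% against 14% it is about 5 points by look 2 (0.35 against 0.40).

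For a strong severity effect, take the 35%/7% split with odds ratio (0.24/0.76)/(0.14/0.86) = 1.94. In 8,000 simulated trials, the probability of crossing by the last look is 0.59 (Fisher) against 0.68 (MH) with Table 11 entries, and 0.65 against 0.73 with nominal cut-offs. A smaller run with Table 11 entries gave 0.08 against 0.13 by look 2 and 0.35 against 0.45 by look 3. The loss is about 5 to 10 points.

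**5. In deaths.** With 18/125 control deaths at the second look (cut-off about 0.0030), Fisher crosses at 39/125 Epo deaths (p = 0.0024; 38 gives 0.0037). Unstratified mid-p crosses at 38 (p = 0.0025). The exact test alone costs one death.

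**The case against.** The strongest reply is that the plan does not commit to Fisher. 'Such as' marks an example, the sentence concerns event rates in general, and the mortality paragraph names no test. A stratified exact test would satisfy the wording. This stands. A reader might infer that deaths will be compared by unstratified Fisher, and the documents do not say so. What remains is that a formal boundary has no fixed test, and the only one named is at odds with the 2% rule elsewhere in the plan.

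A reader might also infer that Fisher halves the error rate. It does not: alone, with correct cut-offs, it gives about 3.6 to 4.3%. Reaching half takes the Table 11 entries as well, or a strong severity effect that the documents do not supply. Protocol 9.4.2 and SAP 5.1.1 raise severity as a possible modifier of the treatment effect, which is not evidence on how strongly it predicts death.

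Nor is death the only endpoint with a boundary. Protocol 9.6 and SAP 9 apply the same boundaries to all other SAEs, with flexibility to continue. Harm detection does not rest on this p-value alone either: a medical monitor reviews every SAE, and the DSMB sees event rates against action thresholds. These points limit the consequence. They do not remove the inconsistency.

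**Conclusion.** The point holds at moderate size. If Fisher is used for deaths, overall two-sided error is about 3 to 4% with correct nominal cut-offs. Discreteness alone accounts for 3.6 to 4.3%; the figure is roughly 3% only under the assumed 35%/7% split with 25% severe, and lower still under a more extreme split. With Table 11 as printed it is about 2 to 3%, and part of that shortfall belongs to the table, not the test.

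The loss in detecting excess deaths is about 2 to 4 percentage points per look with no severity effect (24% against 14%) and about 5 to 10 if severity is strongly prognostic. The monitoring is too cautious, not too liberal: false positives are not inflated and the alpha of the primary efficacy analysis is unaffected.

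It would be wrong to conclude that naming a better test restores 0.05. With the printed entries, a correctly sized test still gives about 3.7%, so both changes are needed. The direction does not depend on the severity assumptions; the larger figures do.

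**What to change.** In Protocol 9.6 and SAP 9:

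- Name one mortality test for all four looks: a two-sided Mantel-Haenszel test, or exact mid-p test, stratified by HIE severity. State the sidedness, which the monitoring text omits.
- Align the shell-table footnote with it, and keep Fisher for SAEs below 2%, as SAP 5.5 already does.
- In the same edit, replace the entries of Protocol Table 11 and SAP Table 6 with nominal cut-offs (about 0.000015, 0.0030, 0.018, 0.044; final digits from the DCC's software).

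Stratifying the interim test by severity only is reasonable: about 70 expected deaths over 15 to 30 sites is roughly 2 to 5 per site even at the last look.

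The cost is a few sentences and one table, since severity is already recorded for randomisation. The small downside is that neither Mantel-Haenszel nor mid-p guarantees strict size at the earliest look, where deaths are few.

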## 7.5 Achieving the sample size

The plan is to enroll and randomize 500 patients over a 36-month period. The 17 sites that were included in the original study proposal cooled a total of 530 HIE infants in the year 2014. From the NEATO phase II randomized controlled trial study, we estimate that at least 40-45% of these infants would be eligible and will consent for a phase III trial, yielding at least 16 enrolled infants per month. With a further conservative estimate of 14 per month allowing for slower enrollment during start-up, we can enroll 500 patients in 36 months.

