Our primary objective for interim analyses is therefore to allow for careful and continued monitoring of mortality and safety outcomes. We propose to conduct formal statistical analysis and inference for mortality at three interim and one final analysis time. We will continue to present mortality and SAE data from all available follow-up data, but we expect most treatment-related safety events to occur within the first three months of follow-up. We will conduct formal safety evaluation at 6, 12, 18, and 24 months following the start of enrollment, where approximately 25, 50, 75, and 100% of the study cohort will have been randomized and followed for at least 3 months. As part of each interim analysis, we plan to monitor mortality as a primary safety endpoint and will control the overall significance level using O'Brien-Fleming boundaries (net alpha=0.05 significance, accounting for three interim and one final analysis). The DSMB will also monitor all other SAEs utilizing the same O'Brien-Fleming sequential monitoring boundaries (**Table 6**) without further adjustment for multiple comparisons but allowing for flexibility to continue the study if the O'Brien-Fleming boundary is reached on a secondary SAE endpoint.

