**Table 6. O'Brien-Fleming Monitoring Boundaries**

Enrollment	Monitoring p-value: Death
25%	0.000014734
50%	0.0030359
75%	0.016248
100%	0.030701

**Data Safety Monitoring Schedule:** Our target enrollment is n=500 which is expected to accrue during the first 4.0 years of the trial. Therefore, we will enroll approximately 83 subjects every 6 months. Our planned DSMB safety analyses will occur every 6 months after trial initiation. At the first safety evaluation, we expect to have 83 subjects enrolled, but would only have discharge outcomes on the first 60 subjects (**Table 7**). Each subsequent 6-month period would increase the number of babies by 83 leading to the following cumulative

number of subjects available for analysis. Safety evaluation will be based on all available follow-up, but we expect most SAEs to occur during the neonatal hospitalization and therefore within one month of age (2-4 weeks) in most cases.

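### The formal mortality looks are tied both to months 6/12/18/24 and to 25/50/75/100% of the cohort, but planned accrual gives 12/29/45/62% on those dates, and the printed boundary p-values are alpha-spending increments

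*Protocol*

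**What the plan says.** Protocol 9.6 and SAP 9 make mortality the primary safety endpoint, with three interim looks and one final look. They schedule "formal safety evaluation at 6, 12, 18, and 24 months following the start of enrollment, where approximately 25, 50, 75, and 100" per cent of the cohort will have been randomized with at least 3 months of follow-up. O'Brien-Fleming boundaries are to hold the overall level ("net alpha=0.05 significance, accounting for three interim and one final analysis"), and the same boundaries apply to the other SAEs.

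The boundaries are in Protocol Table 11 and SAP Table 6. The rows are enrollment percentages (25, 50, 75, 100) and the column is headed "Monitoring p-value: Death". The entries are 0.000014734, 0.0030359, 0.016248 and 0.030701.

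The accrual statements are:
- Protocol 9.6, on efficacy monitoring: at month 34 "we expect to have randomized n=450 of the total n=500 subjects (90% enrollment completed".
- Protocol 9.6, on the monitoring schedule: "Our target enrollment is n=500 which is expected to accrue during the first 4.0 years of the trial", followed by "Therefore, we will enroll approximately 83 subjects every 6 months".
- Protocol Table 12 and SAP Table 7: 60, 143, 226 and 309 infants evaluable for safety at months 6, 12, 18 and 24; 475 at month 36; 500 in the month-42 column.
- SAP 7.5 and Protocol 9.4.5: "The plan is to enroll and randomize 500 patients over a 36-month period", at 14 to 16 infants per month.

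SAP 9 adds: "Our planned DSMB safety analyses will occur every 6 months after trial initiation".

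**The concern.** The months and the percentages cannot both be right, and the choice between them decides which cut-off the DSMB applies.

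If the dates govern, the look treated as final takes place with 500 − 309 = 191 infants (38%) not yet in the safety data, and it uses a cut-off meant for the full cohort. If enrollment governs, the looks fall at the intended information but the stated dates are wrong.

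Under either reading the printed values look like portions of alpha rather than p-value thresholds, so the stated net level of 0.05 would not be the level of the rule as written. These points should be settled before the DSMB sees data by arm.

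**Working it through.** **1. Cohort share on the stated dates.** Inputs: Table 12 counts and N = 500.

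| Month | Stated | Table 12 (1-month safety data) | 83 per 6 months, followed 3 months |
|---|---|---|---|
| 6 | 25% | 60/500 = 12.0% | 41.5/500 = 8.3% |
| 12 | 50% | 143/500 = 28.6% | 124.5/500 = 24.9% |
| 18 | 75% | 226/500 = 45.2% | 207.5/500 = 41.5% |
| 24 | 100% | 309/500 = 61.8% | 290.5/500 = 58.1% |

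The last column is (83/6) × (month − 3). Counting enrollment alone at 83 per 6 months gives 17, 33, 50 and 66%.

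**2. Does any stated rate give 100% at month 24?** Infants followed 3 months = monthly rate × 21:
- 4.0 years: 500/48 × 21 = 219 (44%)
- 450 at month 34: 450/34 × 21 = 278 (56%)
- 83 per 6 months: 290.5 (58%)
- 14 per month: 294 (59%)
- 16 per month: 336 (67%)

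None does. Even enrollment alone at the fastest rate gives 16 × 24 = 384 (77%).

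**3. Accrual duration.** 500/83 × 6 = 36.1 months. A 48-month accrual would be 500/8 = 62.5 per 6 months. So 4.0 years does not fit the rate in the sentence that follows it.

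**4. What the printed boundaries are.** Take the O'Brien-Fleming-type spending function for a two-sided 0.05, α(t) = 4[1 − Φ(z₀.₉₈₇₅/√t)].

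| t | Cumulative α(t) | Increment | Printed | Nominal two-sided p |
|---|---|---|---|---|
| 0.25 | 0.0000147 | 0.0000147336 | 0.000014734 | 0.0000147 |
| 0.50 | 0.0030506 | 0.0030359 | 0.0030359 | 0.0030453 |
| 0.75 | 0.0192986 | 0.0162480 | 0.016248 | 0.0183 |
| 1.00 | 0.0500000 | 0.0307014 | 0.030701 | 0.0440 |

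All four printed entries equal the increments to the digits shown, and they sum to 0.0500. The nominal p-values come from recursive integration of the joint distribution of the four statistics. Two alternatives do not match the table as p-values: classical O'Brien-Fleming (0.0000515, 0.0042, 0.0194, 0.0429) and the spending form 2[1 − Φ(z₀.₉₇₅/√t)] (0.0000886, 0.0055, 0.0215, 0.0411).

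**5. Overall alpha with the printed values used as p-values** (recursive integration): 0.0374 at 25/50/75/100%; 0.0379 at 12/29/45/62%; 0.0384 at 8/25/42/58%.

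**6. Boundaries if the dates govern.** At 12.0, 28.6, 45.2 and 61.8% the same function gives nominal p-values of 2.0 × 10⁻¹⁰, 0.000056, 0.0017 and 0.0082. Cumulative alpha spent by 61.8% is 0.0087. A fifth look at 100% would use 0.0472.

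**7. Size in deaths** (two-sided Fisher's exact test, about 14% mortality in one arm; smallest count in the other arm that crosses):
- Month 24, 309 infants, 22/154 in one arm: 38/155 at 0.0307; 42/155 at 0.0082.
- 250 infants, 18/125: 39/125 with either the printed or the nominal value.
- 375 infants, 26/187: 46/188 printed; 45/188 nominal.
- 500 infants, 35/250: 55/250 printed; 54/250 nominal.

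**The case against.** The best reply is that the boundary tables are indexed only by enrollment. On that reading the cut-off follows the row reached, the months are an approximate forecast that proved wrong, and using the 100% row at 62% would contradict the table's own label. Protocol 7 also leaves DSMB meeting frequency and conduct to a separate document. This reading is reasonable and would put the looks at the intended information. But the text fixes the formal evaluations by month, neither document names the trigger, and approximately cannot stretch from about 60% to 100%. A separate DSMB document does not reconcile the months, percentages and p-values printed here.

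On the mislabelled column, the reply is that a set of cut-offs summing to 0.05 keeps alpha at or below 0.05 under any timing, and that the effect is one death at each of the last two looks. Both points are correct. The error is conservative for type I error and slightly less sensitive to harm.

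Three narrower points also stand. The 12/29/45/62% figures use 1-month safety counts; on the text's 3-month definition the gap is wider. The month-42 entry for 500 infants reflects the six-month grid: from 475 at month 36, the last 25 take 25/(83/6) = 1.8 months, so 500 falls near month 38. Six-monthly DSMB review continues throughout, with absolute SAE thresholds that include one for death.

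**Conclusion.** The concern holds. The stated dates and cohort shares contradict the plan's own accrual figures, by about 38 to 42 percentage points at month 24. The boundary table prints alpha increments under a p-value heading, so the rule as written has an overall level of about 0.037 to 0.038 rather than 0.05.

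The practical effect is modest. Using the 100% cut-off at month 24 moves the crossing point from 42 to 38 deaths of 155 in the illustration. The mislabelling moves it by one death at the 75% and 100% looks and by none at 50%. The differences at the earliest dated looks have little practical effect. The four stated looks do not inflate alpha, and the primary efficacy test is untouched. It should still be corrected, because it concerns the decision threshold for the primary safety endpoint.

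Three assumptions apply. The spending function and its two-sidedness are not stated and are inferred from the four-value match. Information is taken as the proportion of the 500 infants evaluable. The death counts assume about 14% mortality in one arm.

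**What to change.** State in both documents which trigger governs, and replace the printed increments with nominal p-values. Either option works:

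- **(a) Trigger by information.** Hold the formal looks when 125, 250, 375 and 500 infants have been randomized and followed at least 3 months. At 83 per 6 months that is n/(83/6) + 3, or about months 12, 21, 30 and 39. Use nominal p-values of about 0.0000147, 0.0030, 0.0183 and 0.0440.
- **(b) Keep the dates.** Compute each boundary from the spending function at (infants evaluated)/500 and add a formal look on all 500. At Table 12 counts the values are about 2.0 × 10⁻¹⁰, 0.000056, 0.0017, 0.0082 and then 0.0472.

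In either case, name the spending function and its sidedness, state that the remaining six-monthly reviews carry no formal mortality boundary, and reconcile 4.0 years with 36 months and 83 per 6 months.

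The cost is rewording of Protocol 9.6 and SAP 9 and DSMB report programming. Option (a) moves the first formal look from month 6 to about month 12; the six-monthly descriptive reviews still cover that interval.
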